#### 5.6.3.1 Hematology Clinical Chemistry

Laboratory parameters that are graded in CTCAE version 4.03 will be summarized by CTCAE grade. In the summary of laboratory parameters by CTCAE grade, for parameters with CTCAE grading in both high and low direction (*e.g.*, calcium, glucose, magnesium, potassium, sodium), CTCAE in high and low directions will be summarized separately. Subjects with treatment-emergent markedly abnormal laboratory values (TEMAV) will also be summarized. Markedly abnormal is defined as a value that is above or below the normal range and the CTCAE grade increased from baseline by 2 or more grades, except for phosphate which must have shifted by 3 or more grades.

Laboratory test results will be reported in the following methods with three categories: Hematology, liver and renal, and other clinical chemistry.

- Descriptive summary statistics for all parameters and their changes from baseline will be summarized using number of subjects, mean, SD, median, Q1, Q3, and range by visit.
- Shifts from baseline to the worst postbaseline CTC grade will also be presented.

A listing of potential Hy's law cases who meets one of the following criteria: (aspartate aminotransferase or alanine transferase) $>3xULN$  and total bilirubin  $\geq 2xULN$  and alkaline phosphatase  $<2xULN$  at any postbaseline assessment time point during the study will be provided. Parameters selected per Hy's Law definition were provided in [FDA Guidance for Industry Drug Induced Liver Injury: Premarketing Clinical Evaluations, July 2009](#).

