9.3.1 Inclusion Criteria

1. Histological or cytological confirmation of RCC with a clear-cell component (original tissue diagnosis of RCC is acceptable).
2. Documented evidence of advanced RCC.
3. At least 1 measurable target lesion according to RECIST 1.1 meeting the following criteria:
 - Lymph node (LN) lesion that measures at least 1 dimension as ≥ 1.5 cm in the short axis
 - Non-nodal lesion that measures ≥ 1.0 cm in the longest diameter
 - The lesion is suitable for repeat measurement using computed tomography/magnetic resonance imaging (CT/MRI). Lesions that have had external beam radiotherapy (EBRT) or locoregional therapy must show radiographic evidence of disease progression based on RECIST 1.1 to be deemed a target lesion.
4. Male or female subjects age ≥ 18 years (or any age >18 years of age (if that age is considered to be an adult per the local jurisdiction) at the time of informed consent
5. Karnofsky Performance Status (KPS) of ≥ 70 .
6. Adequately controlled blood pressure (BP) with or without antihypertensive medications, defined as BP $\leq 150/90$ mmHg at Screening and no change in antihypertensive medications within 1 week before the Cycle 1/Day 1.
7. Adequate renal function defined as creatinine $\leq 1.5 \times$ upper limit of normal (ULN); or for subjects with creatinine $>1.5 \times$ ULN, the calculated creatinine clearance ≥ 30 mL/min (per the Cockcroft-Gault formula) is acceptable ([Appendix 12](#)).
8. Adequate bone marrow function defined by:
 - Absolute neutrophil count (ANC) $\geq 1500/\text{mm}^3$
 - Platelets $\geq 100,000/\text{mm}^3$
 - Hemoglobin ≥ 9 g/dL

NOTE: Criteria must be met without erythropoietin dependency and without packed red blood cell (pRBC) transfusion within the previous 2 weeks.
9. Adequate blood coagulation function defined by International Normalized ratio (INR) ≤ 1.5 unless participant is receiving anticoagulant therapy, as long as INR is within therapeutic range of intended use of anticoagulants.
10. Adequate liver function defined by:
 - Total bilirubin $\leq 1.5 \times$ ULN except for unconjugated hyperbilirubinemia of Gilbert's syndrome.

- Alkaline phosphatase (ALP), alanine aminotransferase (ALT), and aspartate aminotransferase (AST) $\leq 3 \times \text{ULN}$ (in the case of liver metastases $\leq 5 \times \text{ULN}$), unless there are bone metastases. Subjects with ALP values $> 3 \times \text{ULN}$ and known to have bone metastases can be included.

11. Provide written informed consent.

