Nephritis and Renal dysfunction	Grade 2	Withhold	Administer corticosteroids (prednisone 1-2 mg/kg or equivalent) followed by taper	Monitor changes of renal function
	Grade 3 or 4	Permanently discontinue		
Myocarditis	Grade 1 or 2	Withhold	Based on severity of AE administer corticosteroids	Ensure adequate evaluation to confirm etiology and/or exclude other causes
	Grade 3 or 4	Permanently discontinue		

Table 3 Dose Modification and Toxicity Management Guidelines for Immune-related Adverse Events Associated with Pembrolizumab

Immune-related Adverse Event	Toxicity Grade or Conditions (CTCAEv4.0)	Action Taken with Pembrolizumab	irAE Management with Corticosteroids and Other Therapies	Monitor and Follow-up
All other immune-related AEs	Intolerable/persistent Grade 2	Withhold	Based on type and severity of AE administer corticosteroids	Ensure adequate evaluation to confirm etiology and/or exclude other causes
	Grade 3	Withhold or discontinue based on the type of event. Events that require discontinuation include but are not limited to: Guillain-Barre Syndrome, encephalitis		
	Grade 4 or recurrent Grade 3	Permanently discontinue		

Withholding or permanently discontinuing pembrolizumab is at the discretion of the investigator or treating physician.

For subjects with Grade 3 or 4 immune-related endocrinopathy where withholding of pembrolizumab is required, pembrolizumab may be resumed when the AE improves to Grade ≤ 2 and is controlled with hormonal replacement therapy or metabolic control is achieved (in the case of T1DM).

AE = adverse event; ALT = alanine aminotransferase; AST = aspartate aminotransferase; CTCAE = Common Terminology Criteria for Adverse Events;

GI = gastrointestinal; irAE = immune-related adverse event; IV = intravenous; T1DM = Type 1 diabetes mellitus.

a: If a subject with liver metastasis has Grade 2 AST or ALT at the start of study treatment, and the AST or ALT value increases by $\geq 50\%$ relative to Baseline and lasts for ≥ 1 week, then the subject should permanently discontinue study treatment.

Table 4 shows treatment guidelines for subjects who experience an infusion reaction associated with the administration of pembrolizumab, including premedications.

Table 4 Infusion Reaction Treatment Guidelines

NCI CTCAE Grade	Treatment	Premedication at subsequent dosing

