### 5.3.4 Examination of Subgroups

For efficacy endpoints, the hazard ratio and two-sided 95% confidence interval (CI) for comparing PFS as assessed by the IIR and investigator assessment of either Arm A versus Arm C or Arm B versus Arm C will be presented in forest plots for the subgroups. Median PFS and 95% CIs will be presented for all subgroups. Similar summary and plots will be provided for OS. In addition, the odds ratio and two-sided 95% CIs for comparing ORR as assessed by IIR will be summarized and presented in forest plots. If sample size of subgroup/strata is less than 18 (5% of sample size in the treatment group), the subgroup/strata may be considered to collapse to the closest subgroup/strata as appropriate.

- Age group (<65 years, ≥65 years)
- Sex (male, female)
- Race (White, Asian, all others)
- Geographic region per IxRS (West Europe and North America, Rest of World)
- MSKCC risk group per IxRS (favorable , intermediate, poor risk)
- IMDC risk group (favorable , intermediate, poor risk)
- Number of metastatic sites per IIR (0, 1, 2, ≥3)
- KPS score group (100-90, 80-70)
- Baseline bone metastasis (yes, no)
- Baseline liver metastasis (yes, no)
- Baseline lung metastasis (yes, no)
- PD-L1 status (CPS≥1, CPS<1, not available)
- Prior nephrectomy (yes, no)
- Histologic clear component featuring sarcomatoid (yes, no)

Additional subgroup analyses may also be conducted, if deemed appropriate.

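### The SAP's Hy's law listing leaves out eligible subjects whose postbaseline ALP stays at or above 2xULN, because its ALP condition takes no account of the ALP allowed at entry

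*SAP*

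**What the plan says.** SAP 5.6.3.1 plans a listing of potential Hy's law cases. Three conditions are joined by a plain conjunction: AST or ALT above 3xULN, total bilirubin at or above 2xULN, "and alkaline phosphatase $<2xULN$ at any postbaseline assessment time point during the study will be provided". There is no alternative for a subject who starts with raised ALP. The SAP gives a July 2009 FDA guidance on drug-induced liver injury as its source: "Parameters selected per Hy's Law definition were provided in" that document.

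Protocol 9.3.1, inclusion criterion 10, limits ALP, ALT and AST at entry to 3xULN in general. It then relaxes the limit: "in the case of liver metastases $\leq 5 \times \text{ULN}$), unless there are bone metastases". It adds: "Subjects with ALP values $> 3 \times \text{ULN}$ and known to have bone metastases can be included". No upper limit is given for that last group. The synopsis repeats the criterion.

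The trial expects such subjects. SAP 5.3.4 names "Baseline bone metastasis (yes, no") as a planned subgroup, and liver metastasis likewise. The protocol also recognises that disease can shift liver tests at baseline: Table 3, footnote a, sets a baseline-relative rule that begins "If a subject with liver metastasis has Grade 2 AST or ALT at the start of study treatment". That rule concerns AST and ALT only.

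**The concern.** The entry criterion and the listing filter use the same laboratory test with incompatible limits. A subject may enter with ALP at a level that the listing treats as disqualifying. If ALP stays there, no rise in transaminases and bilirubin, however large, puts that subject in the listing.

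Comparing safety and tolerability with sunitinib is a secondary objective, and Protocol 9.4.2.7 addresses hepatotoxicity with reference to each arm's own dose modification guidelines. The Hy's law listing is the one planned output that looks at transaminases and bilirubin together. Someone reading a short or empty listing could not tell whether combined elevations did not occur or were removed by the ALP condition.

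**Working it through.** The plan states no numerical figure to reproduce on this point. The check applies the two written rules to the same subjects.

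**Inputs**
- Listing rule (SAP 5.6.3.1): listed if (AST or ALT > 3) and (bilirubin ≥ 2) and (ALP < 2), all in multiples of ULN, on postbaseline values.
- ALP part of eligibility (Protocol 9.3.1, criterion 10): eligible if ALP ≤ 3, or ALP ≤ 5 with liver metastases, or any ALP with known bone metastases.

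**Step 1. Same liver signal, different ALP.** Take illustrative subjects who all reach ALT 10xULN and bilirubin 3xULN, with ALP unchanged from entry.

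| ALP (xULN) | Eligible because | ALP < 2? | Listed? |
|---|---|---|---|
| 1.0 | general limit | yes | yes |
| 2.0, 2.5, 3.0 | general limit | no | no |
| 4.0, 5.0 | liver metastases | no | no |
| 3.5, 8.0 | bone metastases | no | no |

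All eight are eligible, and seven are not listed. The rows at 2.0 to 3.0 show that the gap does not depend on metastases.

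**Step 2. ALP falls on study.** If ALP is 1.8xULN when the other two values are raised, all eight are listed. The filter acts on postbaseline ALP, not on the entry value.

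**Step 3. Timing of the three conditions.** The SAP does not say whether they must be met at the same assessment. Take one subject with two postbaseline visits:
- Visit 1: ALT 1, bilirubin 0.5, ALP 1.8.
- Visit 2: ALT 10, bilirubin 3, ALP 2.6.

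If the conditions must coincide, neither visit meets all three and the subject is not listed. If each may be met at any visit, the subject is listed. Under either reading, a subject whose ALP never falls below 2xULN after baseline is left out.

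**Step 4. Other planned outputs.** CTCAE summaries and shift tables (SAP 5.6.3.1) take one parameter at a time. The markedly-abnormal summary in the same section generally needs a rise of at least two grades, so a subject who starts at Grade 2 AST or ALT and reaches Grade 3 does not count. Adverse event listings (SAP 5.6.2 and 5.6.2.1) depend on what is reported as an event. Per-subject listings of summarized variables (SAP 5) contain the raw values but do not screen for the combination.

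**Step 5. Possible size.** The share of subjects with ALP at or above 2xULN is not given. If it is 5% to 15% (an assumption):
- per arm: 0.05 × 350 = 17.5 and 0.15 × 350 = 52.5, about 18 to 53;
- overall: 0.05 × 1050 = 52.5 and 0.15 × 1050 = 157.5, about 53 to 158.

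These are subjects who could fall outside the filter, not missed cases. If 0.5% to 1% of them had a combined elevation (a second assumption) and all kept ALP at or above 2xULN throughout, the expected number missed per arm would be 17.5 × 0.005 ≈ 0.09 to 52.5 × 0.01 ≈ 0.5.

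**The case against.** The strongest reply has three parts.

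First, the definition is attributed to regulatory guidance. That guidance is not among the documents reviewed, so no departure from it can be shown. This stands. The point is not that the definition is misquoted, but that it is applied to this population without a supplement.

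Second, the injury would not be hidden. Under Protocol 9.5.1.4.1, a laboratory abnormality that leads to intervention, or to withholding or stopping study drug, should be considered an adverse event. Tables 1, 2 and 5 tie treatment-related Grade 3 toxicity to interruption, subject to their footnotes, and Table 3 names AST, ALT and bilirubin elevations. Events of Grade 3 or above, serious events, and those leading to dose changes or discontinuation are listed by subject. SAP 6 has the DMC review safety data with treatment information. This also stands, and it limits the consequence. It does not supply a combined screen.

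Third, no test, threshold or decision rule uses the listing, and the SAP plans no count or between-arm comparison from it. This stands too. A reader might infer that losing even one case would change the trial's conclusion, but nothing in the documents supports that.

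**Conclusion.** The point holds as a narrow safety-reporting gap. Followed exactly, the filter omits eligible subjects who have the combined transaminase and bilirubin elevation and whose postbaseline ALP stays at or above 2xULN, and no other planned output screens for that combination. Alpha, power and the efficacy analyses are unaffected.

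A reader might go further and infer that the listing is blind to everyone with bone or liver metastases, or that raised ALP at entry rules a subject out for good. Neither follows. The rule does not mention metastases, those with ALP below 2xULN are screened like anyone else, and the value tested is postbaseline.

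The conclusion rests only on the wording of the two rules. Its practical size is unknown. The counts above depend on an assumed prevalence of raised ALP, and the expected number of missed cases on a second assumption; on those figures it is below one per arm. That makes this a worthwhile, inexpensive improvement rather than a serious defect.

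**What to change.** In SAP 5.6.3.1, list all subjects with postbaseline AST or ALT above 3xULN and total bilirubin at or above 2xULN regardless of ALP. Flag the subset with ALP below 2xULN, which keeps the present definition and its cited source intact. For each listed subject show baseline and concurrent ALP, baseline AST and ALT, and bone and liver metastasis status. Baseline AST and ALT matter because criterion 10 allows up to 5xULN with liver metastases, so some subjects may enter already above the transaminase threshold. Give both counts by arm.

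The same edit should say whether the conditions must be met at one assessment, and should remove the lead-in that announces several alternative criteria when only one combined criterion follows.

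The cost is a small revision of the SAP text and one listing filter. All four tests are already collected under Protocol Table 6. The downside is a few extra cases with a cholestatic or disease explanation to review.

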#### 5.6.3.2 Urinalysis

Proteinuria: Shifts from Baseline to worst postbaseline for proteinuria determined by dipstick (negative, trace, 1+, 2+, 3+, 4+) will be presented by treatment arms. The urinalysis results from UPCr or 24-hour urine protein ( $< 1.0$ ,  $1.0-3.5$ ,  $> 3.5$  g/24 hrs according to CTCAE grade) will also be summarized (frequency and percentage) by worst Grade.

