9.4.2.2 Management of Proteinuria

Regular assessment of proteinuria should be conducted as detailed in the Schedule of Procedures/Assessments. Guidelines for assessment and management of proteinuria are as follows:

Grading of Proteinuria

- Grading according to CTCAE v4.03 will be based on the 24-hour urinary protein result if available.

Management of Proteinuria

- Management of lenvatinib/sunitinib administration will be based on the grade of proteinuria according to the respective treatment arm's Dose Modification Guidelines.
- In the event of nephrotic syndrome, lenvatinib/sunitinib must be discontinued.

Detection and Confirmation

1. Perform urine dipstick testing per the Schedule of Assessments (Table 7 and Table 8)
2. A 24-hour urine collection (initiated as soon as possible and at least within 72 hours) or an immediate spot urine protein-to-creatinine ratio (UPCR) test is required in the following situations:
 - The first (initial) occurrence of $\geq 2+$ proteinuria on urine dipstick while on study drug
 - A subsequent increase in severity of urine dipstick proteinuria occurring on the same lenvatinib/sunitinib dose level
 - When there has been a lenvatinib/sunitinib dose reduction and at the new dose level the urine protein dipstick result is $\geq 2+$
3. A 24-hour urine collection (initiated as soon as possible and at least within 72 hours) to verify the grade of proteinuria is required when UPCR is ≥ 2.4 .

Monitoring

- Urine dipstick testing for subjects with proteinuria $\geq 2+$ should be performed on Day 15 (or more frequently as clinically indicated) until the results have been 1+ or negative for 2 consecutive treatment cycles.

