9.4.2.6 Management of Blood Glucose and Lipids

Hyperglycemia, hyperlipidemia and hypertriglyceridemia are recognized class effects of rapamycin derivatives, including everolimus. Glycemic and lipid control should be optimized before starting a subject on this study. Blood glucose will be monitored as specified in the Schedule of Procedures/Assessments. For subjects with blood glucose > ULN, a fasting (> 6h, water only) blood glucose sample will be obtained. Grading will be based on the fasting blood glucose result. The choice of hypoglycemic agent should be individualized to the subject's clinical circumstances and follow standard medical practice.

Dose alterations of everolimus may be required in accordance with prescribing information.

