## 8.2 Safety and Disease History Data Handling

### 8.2.1 Visit Windows for Safety Analyses

Visit windows will be defined to be upper and lower bounds of one day of the scheduled visit, following the protocol, which states that efforts should be made to conduct laboratory assessments and administer treatment on the day scheduled ( $\pm 1$  day). In the calculation of descriptive statistics for laboratory values and vital signs, if a visit has multiple observations, the observation closest in date and time to the target visit day will be used in the analysis. If two or more observations have the same distance to the target visit day, the one that has the highest CTCAE grade or is furthest away from the normal range will be used.

The purpose of this windowing is to provide a single record per subject per visit for the calculation of descriptive statistics per scheduled visit, and change from baseline per visit. Other safety analyses (e.g., worst grade laboratory results) will include all observations.

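### The SAP's worst-grade laboratory tables let a UPCR superseded by a 24-hour collection, or a non-fasting glucose followed by a fasting repeat, set a higher grade than the protocol's grading rule gives

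*SAP*

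**What the plan says.** **Proteinuria, protocol.** Section 9.4.2.2 states: "Grading according to CTCAE v4.03 will be based on the 24-hour urinary protein result if available". A dipstick of 2+ or more leads, in the listed situations, to either a 24-hour collection or an immediate UPCR. A further 24-hour collection "to verify the grade of proteinuria is required when UPCR is" 2.4 or higher. The Synopsis says the same.

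**Proteinuria, SAP.** Section 5.6.3.2 says that "The urinalysis results from UPCr or 24-hour urine protein", banded at <1.0, 1.0-3.5 and >3.5 g/24 h, "will also be summarized (frequency and percentage) by worst Grade". It does not say which result counts when a subject has both.

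**Glucose, protocol.** A value above the upper limit of normal calls for a fasting sample. Section 9.4.2.6 then says: "Grading will be based on the fasting blood glucose result". The Synopsis version of that sentence names CTCAE v4.03 explicitly.

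**Glucose, SAP.** Section 5.6.3.1 says: "Laboratory parameters that are graded in CTCAE version 4.03 will be summarized by CTCAE grade". It names glucose among the examples. It adds: "Shifts from baseline to the worst postbaseline CTC grade will also be presented". The same section defines treatment-emergent markedly abnormal values (TEMAV) by the rise in CTCAE grade. It makes no mention of fasting.

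**Records used, SAP.** Section 8.2.1 says: "Other safety analyses (e.g., worst grade laboratory results) will include all observations".

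**The concern.** For both analytes the protocol sets up a first test and then a second test on which the grade rests. A worst-grade rule over every record keeps the first test in play after the second has replaced it, so a verifying result that reads lower has no effect on the table.

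The analytes matter in this trial. Protocol Section 7.1.2 reports proteinuria as the most common Grade 3 or 4 event on single-agent lenvatinib in Study 205 (10 subjects, 19%). Section 9.4.2.6 calls hyperglycemia a recognized class effect of rapamycin derivatives, including everolimus. At stake is whether the laboratory grade tables agree with the grading basis that the protocol itself lays down.

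**Working it through.** There is no planned figure to reproduce. This is a comparison of two derivation rules.

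**Inputs**
- Bands: <1.0, 1.0-3.5, >3.5 g/24 h (SAP 5.6.3.2).
- Verification trigger: UPCR of 2.4 or more (protocol 9.4.2.2).
- Protocol rule: band of the 24-hour value if there is one, otherwise band of the UPCR.
- SAP rule as written: highest band among all values (SAP 5.6.3.2 with 8.2.1).

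**Step 1: apply both rules to example values.** The values are illustrative and are not trial data.

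| UPCR | 24-hour, g | Protocol rule | SAP rule | Same? |
|---|---|---|---|---|
| 4.0 | 2.0 | 1.0-3.5 | >3.5 | no |
| 3.6 | 2.0 | 1.0-3.5 | >3.5 | no |
| 4.0 | 3.4 | 1.0-3.5 | >3.5 | no |
| 2.6 | 0.9 | <1.0 | 1.0-3.5 | no |
| 2.6 | 2.0 | 1.0-3.5 | 1.0-3.5 | yes |
| 3.0 | 3.8 | >3.5 | >3.5 | yes |
| 1.5 | none | 1.0-3.5 | 1.0-3.5 | yes |

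**Step 2: direction.** For a pair, the SAP rule takes max(UPCR band, 24-hour band), which is never below the 24-hour band. It is higher exactly when the UPCR falls in a higher band. Any disagreement is therefore upward.

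**Step 3: where a pair should exist.** Since 2.4 < 3.5, every UPCR in the top band is one for which the protocol requires a 24-hour collection. The same holds for UPCR values from 2.4 to 3.5 in the middle band. Below 2.4 a UPCR may stand alone, and the two rules then agree.

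**Step 4: glucose.** The sample that prompts a fasting repeat is itself above the normal limit. If it carries a higher CTCAE grade than the repeat, the protocol grades on the repeat, while a worst grade over all observations keeps the trigger value. The TEMAV summary inherits this, because it counts subjects whose grade rose by 2 or more from baseline.

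**The case against.** **The SAP does not say that the higher of a pair wins.** The word joining the two urine tests could mean whichever applies. The all-observations sentence in Section 8.2.1 is set against the rule of one record per subject per visit, so its purpose may be only to keep unscheduled records. SAP Section 9 also leaves derivation rules to separate documents, which could contain a precedence rule. This stands in part: precedence between assays is never addressed. But Section 8.2.1 names worst-grade laboratory results and admits every record, so a specification that discarded a superseded UPCR would depart from the SAP's own wording.

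**One g/24 h scale for both tests is not an error.** Protocol Table 6 allows either test to quantify 24-hour excretion. That is correct, and the point does not rest on it.

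**The protocol rules sit under toxicity management, and protocol Section 9.7.1.8.3 itself asks for shifts to the worst postbaseline grade without a 24-hour or fasting condition.** It follows that worst grade is not a departure from plan, and a reader who infers that SAP Section 7 hides an undeclared change goes further than the text allows. The question is only which values are eligible for grading. On that, the protocol's sentences are worded as grading rules, and the SAP tables report CTCAE grades.

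**Worst observed grade is a cautious convention, and a later, lower value may reflect treatment interruption.** This is fair for separate episodes. It is a reason to apply precedence within a pair and then take the worst across episodes.

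**Conclusion.** The point holds in a limited form. Where a UPCR and its 24-hour collection both exist, or a triggering glucose and its fasting repeat, the SAP as written can report a higher grade than the protocol's rule, and never a lower one. A UPCR of 2.4 or more that was never verified may still be graded, because the protocol uses the 24-hour result only if available, but the table would not show that the grade is unverified.

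The effect is confined to descriptive laboratory grade tables, including the glucose TEMAV summary. It does not touch efficacy results or investigator-graded adverse events. The conclusion assumes that the unseen programming specifications follow the SAP text.

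Four stronger readings are tempting but unsupported:
- **Unverified values set the reported grade in general.** They do so only when they are the worst value on record.
- **A percentage overcount of severe cases.** That needs a rate at which 24-hour collections fail to confirm the UPCR, and the documents give none.
- **Distortion of the comparison between arms.** The proteinuria rules are the same for lenvatinib and sunitinib, and nothing in the documents gives the size or direction of a difference.
- **Hypocalcemia will be graded on uncorrected calcium.** SAP Section 5.6.3.1 is silent on albumin correction and does not rule it out.

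**What to change.** In SAP 5.6.3.2, state that a 24-hour result supersedes its paired UPCR before the worst grade is taken, that UPCR is used only when no 24-hour result exists, and that grades resting on UPCR alone are flagged.

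In SAP 5.6.3.1, with a matching exception in 8.2.1, state that where a fasting repeat exists hyperglycemia is graded on it, and that non-fasting values are shown separately. The same rule should feed the TEMAV summary.

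The cost is a few sentences and one derivation rule in the laboratory dataset. The small downside is that pairing by date must be defined. For urine, the protocol gives 72 hours to start the collection, which offers a natural window. For the fasting glucose it gives no time limit, so the SAP must choose one and say so. The pairing rule should also say how it fits with the preference for central over local results in SAP 5.6.3, so that a fasting repeat run locally is not displaced by a non-fasting central value.
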